## 11.1 Sample Size

Interim analyses at a group level (immediate intervention vs delayed intervention) start with a small number of participants (e.g. n=20) and are conducted sequentially every approximately between 4-10 participants thereafter, up to a maximum of approximately n=150. Prespecified thresholds are used to trigger a potential modification of the intervention (e.g. assessed using Bayes factors which compare different hypotheses. If the intervention is shown to be significantly more effective than control (assessed using Bayes factors which compare different hypotheses) before reaching the max n=150 participants, then the optimisation study may conclude early and a follow-up pragmatic RCT, testing clinical effectiveness of the optimised intervention, can be initiated (a separate ethics application will be submitted for such a study). Our thinking around this has been informed by initial power estimates based on an effect size of  $d= 0.63$  for the primary outcome, pooled from three RCTs of this intervention Horsch et al, 2017; Iyadurai et al., 2018; Kanstrup, Singh et al. 2021). Our simulations estimate 84% power to find strong evidence for the intervention by the time the maximum sample size (n=150) is reached.

## 11.2 Data Set for Analysis

All analyses will be conducted on an intention to treat (ITT) basis. The ITT is defined as all randomised participants.

## 11.3 Description of Statistical Methods

[name] [name], and [name] will work with collaborators and statisticians ([name] and [name], [name] and [name] to develop the statistical analysis plan and to analyse the data. A pre-specified analysis script will be preregistered prior to data analysis (e.g., on the Open Science Framework).

### 11.3.1 Study Design Analysis

Ongoing sequential analysis using Bayesian statistical approaches will be used to evaluate the study design based on the primary outcome (difference in the number of intrusive memories in week 4 for groups of participants. The analysis will control for the number of intrusive memories during the run in week. Exploratory data analysis will be used to investigate the distribution of the primary outcome measure. Patterns of missing data will be explored and will be imputed as necessary. In the case where we see excess zeros (i.e., zero inflation) we will explore treating this with the use of an alternative statistical model (e.g., zero inflated Poisson GLM, negative binomial). This is further explained in the statistical analysis plan for designing the study.

### 11.3.2 End of study Analysis

Standard statistical methods will be used to analyse the complete trial data. The sections below (11.3.3 – 11.3.5) give a brief overview of these planned analyses.

Outcome measures will be tested for assumptions of the planned analyses, and where assumptions are violated (e.g., normality of residuals), data will be either transformed or analysed using a non-parametric test.

Sensitivity analyses will be conducted to examine whether analytical decisions (e.g., the exclusion of outliers or inclusion of covariates in analyses) influences the results.

For tertiary analyses (section 11.3.3 below), a combination of descriptive and qualitative analyses will be used. This end of study analysis will be conducted by the University of Nottingham.

### 11.3.3 Analysis of Primary Objective:

A between-groups analysis will be used to test the difference in the number of intrusive memories in week 4 (i.e. from Day 22 to 28) between the immediate intervention and delayed intervention groups. The analysis will control for the number of intrusive memories during the run-in week.

### 11.3.4 Analysis of Secondary Objectives:

As all measures will be repeatedly measured, multilevel modelling will be used to examine the group comparison at 4th week and derive the change estimate from baseline to each follow-up time, with patient as level two analytical unit, baseline measure, treatment arm, following up time and the interaction of arm  $\times$  time as covariate.

A within-group analysis will be used to test the change in the number of intrusive memories from the run-in week to week 4 (Day 22 to 28) in the immediate intervention group.

A within-group analysis will be used to test the change in the number of intrusive memories from week 4 (Day 22 to 28) to week 8 (Day 50 to 56+7 days) in the delayed intervention group.

Between-groups analyses will be used to test for differences in other secondary outcomes at 4 weeks between the immediate intervention and delayed intervention groups: intrusive memory ratings of distress and disruption to concentration / functioning; symptoms of post-traumatic stress, anxiety, depression and insomnia; sickness absence; work engagement and burnout; intention to leave job; functioning and quality of life.

Within-group analyses will be used to test the change in other secondary outcomes (listed above) from baseline to 4 weeks in the immediate intervention group.

Within-group analyses will be used to test the difference in other secondary outcomes (listed above) from 4 weeks and 8 weeks in the delayed intervention group.

Within-group analyses will be used to test if changes in secondary outcome measures are maintained at 8 weeks post intervention onset in the immediate intervention arm.

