### **2.2 Secondary Objectives**

- To determine if access to the intervention plus symptom monitoring for 4 weeks can reduce the number of intrusive memories from run-in week (pre-intervention) to week 4 (post intervention; within-group comparison in the immediate intervention arm) and from week 4 (pre intervention) to week 8 (post intervention; within-group comparison in the delayed intervention arm)
- To determine if immediate access to the intervention plus symptom monitoring for 4 weeks (immediate intervention arm), compared to usual care for 4 weeks (delayed intervention arm), can reduce intrusive memory ratings of distress and disruption to concentration/functioning; symptoms of post-traumatic stress, anxiety, depression and insomnia; sickness absence; burnout; intention to leave job; and improve work engagement, functioning and quality of life at 4 weeks(i.e. between-groups comparison).
- To determine if access to the intervention plus symptom monitoring for 4 weeks, can reduce intrusive memory ratings of distress and disruption to concentration/functioning; symptoms of post-traumatic stress, anxiety, depression and insomnia; sickness absence; burnout; intention to leave job; and improve work engagement, functioning and quality of life from baseline (pre intervention) to 4 and 8 weeks (post intervention; within-group comparison in the immediate intervention arm) and from 4 weeks (pre intervention) to 8 weeks (post intervention; within-group comparison in the delayed intervention arm).

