## **4.0 Study Population**

### **4.1 Inclusion Criteria**

Potential participants will be included if they meet the following criteria:

- Aged 18 or above
- Able to read, write and speak in English
- Worked in a clinical role in an NHS Intensive Care Unit or equivalent during the COVID-19 pandemic (e.g. as a member of ICU staff or deployed to work in the ICU during the pandemic).
- Experienced at least one traumatic event related to their work during the COVID-19 pandemic, meeting criterion A of the DSM-5 criteria for PTSD: "exposure to actual or threatened death, serious injury, or sexual violence" by "directly experiencing the traumatic event(s)" or "witnessing, in person, the event(s) as it occurred to others"
- Have intrusive memories of the traumatic event(s)
- Experienced at least three intrusive memories in the week prior to screening
- Have internet access
- Willing and able to provide informed consent and complete study procedures (including briefly listing their intrusive memories (without going into any detail), and playing the computer game Tetris® with particular mental rotation instructions and completing an online intrusive memory diary).
- Willing and able to be contacted by the research team during the study period

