### **4.2 Exclusion Criteria**

Potential participants will be excluded if they meet the following criteria:

- Have fewer than three intrusive memories in the run-in week

We will not exclude those undergoing other treatment for PTSD or its symptoms, so the study is as inclusive as possible to meet the challenges ICU staff are facing during the COVID-19 pandemic.

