#### 5.4.3 Rescreening

The study permits the re-screening (after the end of the screening period) of participants who have consented to participate in the study but are not subsequently randomised into the study for any reason (e.g. the participant had fewer than 3 intrusive memories during the run-in week, but may have more intrusive memories at a later time). The participant will be assigned a new participant identification number, and the screening procedures must be performed again.

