# **3 Statistical Principles**

## **3.1 Confidence intervals and P values**

All applicable statistical tests in frequentist modelling will be 2-sided and will be performed using a 5% significance level. No multiplicity adjustments will be undertaken as there is only one primary outcome, and analysis for secondary outcomes aim to support primary analysis results (European Medicines Agency, 2016).

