#### 5.2.5 Analysis of secondary outcomes

To quantify treatment effect estimate and within arm change between each measuring time for the number of intrusive memories at week 8 and other secondary outcome measures. MLM will be performed with baseline measure, binary arm status, following up time and interaction of arm  $\times$  time included as fixed effect covariates, participant as level 2 analytical units (European Medicines Agency, 2013). ML linear regression will be used for normally distributed continuous data (Vickers and Altman, 2001), ML logistic regression will be used for binary outcomes. Multilevel Poisson regression will be performed for count data. Skew continuous measure will be transformed for ML linear regression model if needed with reference on data exploratory results, (see for example Manning and Mullahy, 2001; Ives, 2015; Curran-Everett, 2018). For count data, ZIP model will be performed if there are extreme 0 counts or negative binomial model will be conducted if the data is over

dispersed. The treatment effect estimate and its 95% CI together with significance level for between group comparison will be derived from MLM, the estimate and its 95% CI will be presented for the estimate of within group change from baseline to each follow-up time.

If MLM result showed non-significant level-two variance estimate, or any model convergence issues, conventional single level regression will be performed with cluster-robust standard error reported for treatment effects estimate.

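### The run-in count is both the entry gate and the starting value of the immediate-arm run-in to week-4 test, so that test will declare a reduction too often when the intervention does nothing

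*Protocol*

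**What the plan says.** **Entry.** Protocol 4.1 requires: "Experienced at least three intrusive memories in the week prior to screening". Protocol 4.2 then excludes those who: "Have fewer than three intrusive memories in the run-in week". Protocol 5.5 and SAP 2.2.1 randomise only people with three or more in that week's diary. Protocol 5.4.3 allows another attempt: "The study permits the re-screening (after the end of the screening period) of participants who have consented". Its example is that "the participant had fewer than 3 intrusive memories during the run-in week, but may have more intrusive memories at a later time".

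**Use of the run-in count as a starting value.** The first secondary objective (Protocol 2.2, repeated in SAP 1.2) is to determine whether access to the intervention "can reduce the number of intrusive memories from run-in week (pre-intervention) to week 4", within the immediate arm. Protocol 11.3.4 serves it with: "A within-group analysis will be used to test the change in the number of intrusive memories from the run-in week to week 4".

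**Error level and reporting.** SAP 3.1: "All applicable statistical tests in frequentist modelling will be 2-sided and will be performed using a 5% significance level". For within-arm change, SAP 5.2.5 says that "the estimate and its 95% CI will be presented for the estimate of within group change from baseline to each follow-up time".

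Neither document mentions regression to the mean or limits how this one-arm result may be read.

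**The concern.** For a given person, a weekly count retained only if it is at least 3 averages above that person's usual rate. The week-4 count is not filtered in this way. The mean therefore falls from run-in to week 4 even if nothing changes, and a test of no change has the wrong null value. Recovery over time would push the same way, and a one-arm comparison cannot separate either from an effect.

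At stake is the first-listed secondary objective. SAP 3.1 says that secondary analyses are there to back up the primary result, and SAP 1 says that the trial informs a later definitive one. A significant pre/post fall that partly reflects the entry rule is not independent backing.

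**Working it through.** **Inputs from the documents.** Two-sided 5% (SAP 3.1), so 2.5% in the direction of a reduction. At least 3 in the week before screening and at least 3 in the run-in (Protocol 4.1, 4.2). About 75 per arm (Protocol 3.1).

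**Step 1: direction, by formula.** If a person's weekly count is Poisson with rate λ, then E[X | X ≥ 3] = λ × P(X ≥ 2) / P(X ≥ 3), which always exceeds λ.
- λ = 3: 3 × 0.8009 / 0.5768 = 4.17
- λ = 5: 5 × 0.9596 / 0.8753 = 5.48
- λ = 10: 10 × 0.9995 / 0.9972 = 10.02

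Expected week 4 with no effect is λ. The artefact is large near the threshold and fades as rates rise.

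**Step 2: size, by simulation.** These are assumptions, since the documents give no count distribution:
- person rates are gamma with shape 1;
- weekly counts are Poisson, with or without extra gamma week-to-week variation of CV 0.5;
- no effect and no trend, n = 75, 10,000 trials per cell;
- paired t-test on raw counts, or on log(1 + count).

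*Nominal level first.* With no entry rule, a reduction is declared in 2.0–3.0% of trials, so the 2.5% is reproduced.

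*With both entry checks.* In each cell, the first figure is for Poisson variation only and the second for CV 0.5:

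| Mean before selection | Run-in mean | Week-4 mean | Reduction declared, raw | Reduction declared, log |
|---|---|---|---|---|
| 3 | 6.7 / 7.4 | 6.1 / 6.3 | 27% / 38% | 67% / 90% |
| 5 | 8.8 / 9.7 | 8.4 / 8.8 | 10% / 16% | 35% / 61% |
| 8 | 11.8 / 12.9 | 11.6 / 12.2 | 6% / 7% | 18% / 33% |
| 12 | 15.9 / 17.1 | 15.7 / 16.6 | 4% / 4% | 11% / 19% |
| 20 | 23.9 / 25.3 | 23.8 / 24.9 | 3.1% / 3.3% | 7% / 11% |

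The spurious week-4 to run-in ratio is 0.91–0.99 at means 5–12 and as low as 0.85 at mean 3. The log column matters because Protocol 11.3.2 allows transformation when assumptions fail.

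*Other assumptions.* Log-normal weekly variation gave 4–13% on raw counts at means 5–12 and 2.7–3.5% at mean 20. Adding weekly autocorrelation of 0.6 gave 18% at mean 5. With 40 in the arm, mean 5 gave 8–12%.

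**Step 3: which feature drives it.** At mean 5 with CV 0.5, the run-in cut-off alone gives 25%, and both cut-offs give 16%. The pre-screen check lowers the inflation by removing low-rate people. If half of run-in failures rescreen once, the rate hardly moves (16.4% against 15.6%).

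**Step 4: contrasts that hold their level.** Same selection, no effect, rate of declaring a reduction:
- immediate minus delayed arm in run-in to week-4 change: 2.1–2.6%;
- week 4 between arms, adjusted for run-in (log-scale ANCOVA): 2.2–2.9%, or 4.7–5.6% two-sided;
- delayed arm, week 4 to week 8: 1.8–3.6%.

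**Step 5: a contrast to avoid.** The delayed arm's week-4 to week-8 change, set against its own run-in to week-4 change, favours harm in 3–9% and benefit in 0.3–1.5% at means 5–12.

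**The case against.** The strongest reply is that the SAP already does much of what is needed. SAP 5.2.5 attaches the significance level to the between-group comparison and gives within-group change only as an estimate with CI. SAP 2.4 frames secondary superiority as immediate over delayed. The run-in and week-4 counts of both arms already form the primary analysis (SAP 5.2.2), and SAP 5.2.1 and 5.2.6 tabulate them. All of this stands, so it would be wrong to say that the delayed-arm control goes unused. It does not close the point. Protocol 11.3.4 still says test, the objective still says determine, and a 95% CI that excludes no change is the same 5% test.

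It is also fair that the size is assumed, that it is near nominal on raw counts at about 20 a week, and that the planned multilevel Poisson, zero-inflated or negative binomial model was not itself simulated.

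A reader might infer three stronger things.
- *That selection in two successive weeks is the cause.* Step 3 shows otherwise. The first count is also a report at screening, and the schedule does not make the two weeks adjacent.
- *That a positive result would be no evidence at all.* A fall much larger than the artefact could not be explained by selection alone, although natural recovery would still have to be ruled out.
- *That the trial's main result is compromised.* The randomised comparison adjusted for run-in keeps its level.

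**Conclusion.** The point holds for one secondary analysis. Because the run-in week is both gate and starting value, the immediate-arm run-in to week-4 change is biased towards a reduction. That direction follows from the entry rule.

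The size is conditional. With gamma-Poisson counts, 75 participants, no effect and no trend, a reduction is declared in about 4–16% of trials on raw counts at pre-selection means of 5–12, rather than 2.5%. It is higher on a log scale or nearer the threshold, and 3–4% at a mean of 20. Natural recovery is not in these figures and would add to them.

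The primary comparison and the delayed arm's week-4 to week-8 change are not affected by this selection. The wording should be changed, because as it stands the protocol rests a claim about the intervention on a test with the wrong error rate.

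**What to change.** 1. In Protocol 11.3.4, and in the matching line of the synopsis, replace the test of the immediate-arm run-in to week-4 change with an estimate and 95% CI labelled descriptive. Put the same label in SAP 5.2.5.
2. Show the delayed arm's run-in to week-4 change beside it.
3. State that any conclusion that the intervention reduces intrusive memories comes from the randomised between-arm contrast: arm × time, or week 4 adjusted for the run-in count.
4. Add one sentence saying that a within-arm fall from the run-in week includes regression to the mean from the entry rule and any natural recovery.
5. Do not benchmark the delayed arm's week-4 to week-8 change against its own run-in to week-4 change, because that reference carries the same artefact.

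Cost: wording in two documents, with no new data and no new model, since both arms keep the week-4 diary and the SAP model already has the arm × time term. One secondary claim becomes more cautious.

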#### **11.3.5 Analysis of Tertiary Objectives**

Acceptability questionnaires will be reported using descriptive statistics. Free text comments will be analysed thematically. Questionnaire and demographic data will be used to guide sampling for the semi-structured interviews.

Interview data will initially be thematically analysed using an inductive thematic, constant comparison approach based on grounded theory (Glaser and Strauss 1967). Once a thematic analysis has been carried out and key themes identified, data will be explored for suitability in relation to normalisation process theory (or an alternative framework drawn from implementation science, addressing key aspects such as the intervention's design and fit within clinical practice, if more suitable). This will be complemented by the questionnaire data, which will provide quantitative data that includes aspects of normalisation process theory. Normalisation process theory is a sociological theory developed and tested to understand the implementation of new ways of working (including technology) in health care, including depression and in primary care (May et al. 2009). It is likely that we will use normalisation process theory to explore implementation of the intervention. However, using a predetermined analytical framework precludes a more inductive approach and risks the exclusion of relevant insight that is not discernible through that particular analytical lens. For this reason, choice of analytical framework will be informed by its appropriateness to the data (MacFarlane and O'Reilly de Brun 2012).

Both the questionnaire and interview data will be used to develop an inductive analysis of the value and implementation of the intervention. This type of inductive analysis will further our understanding of how the intervention is used and if changes could be made to enhance its implementation and facilitate its adoption.

Descriptive statistics will be used to summarise data regarding support from managers and family/friends and changes to health and work in the two groups.

Descriptive statistics will be used to summarise rates of recruitment, intervention use/adherence, outcome measure completion and

participant attrition.

Descriptive statistics will be used to summarise quantitative data regarding intervention acceptability (feedback questionnaire)

Qualitative interview data will be thematically analysed using an inductive thematic, constant comparison approach based on grounded theory (Glaser and Strauss 1967).

## **12.0 Quality Control and Quality Assurance**

Regular monitoring will be performed to verify that the study is conducted and data are generated, documented and reported in compliance with the protocol, GCP and the applicable regulatory requirements. The Investigator will allow the monitor to carry out study monitoring at regular intervals, depending on the recruitment rate, and at times arranged by mutual agreement.

Quality assurance representatives from the Sponsor or P1vital may visit to carry out an audit of the study in compliance with regulatory guidelines and relevant standard operating procedures.

The Investigator will allow monitors and other persons responsible for audits to:

- meet all members of his / her team involved in the study,
- consult all of the documents relevant to the study,
- directly access source documents to check,
- verify that the study is carried out in compliance with the protocol and local regulatory requirements.

All information dealt with during these visits will be treated as strictly confidential.

## **13.0 Data Monitoring Committee**

An independent data monitoring committee including a psychologist, clinician, statistician and other appropriate members from the expert advisory panel will be appointed. The Data Monitoring Committee will review trial data and will advise the Sponsor whether changes to the protocol are advisable in light of safety, optimisation, recruitment and retention of participants and/or sample size.

Any changes to optimise the intervention procedures will be decided by members of the Data Monitoring Committee.

## **14.0 Regulatory and Ethical Obligations**

### **14.1 Regulatory Framework**

The trial will be conducted in compliance with the principles of the Declaration of Helsinki (1996 – the author should confirm which version is preferred by the sponsor at the time of writing), the principles of GCP and in accordance with all applicable

national and international regulatory requirements, including but not limited to the Research Governance Framework and the Medicines for Human Use (Clinical Trial) Regulations 2004, and any subsequent amendments.

